6.1.6 Pregnancy

Pregnancy in a study subject must be reported to AbbVie within 1 working day of the study site becoming aware of the pregnancy. Subjects who become pregnant during the study must be discontinued (Section 5.4.1). Pregnancies will be collected from the date of the first dose through 150 days following the last dose of study drug.

Information regarding a pregnancy occurrence in a study subject and the outcome of the pregnancy will be collected.

Pregnancy in a study subject is not considered an AE. However, the medical outcome of an elective or spontaneous abortion, stillbirth, or congenital anomaly is considered a SAE and must be reported to AbbVie within 24 hours of the study site becoming aware of the event.

6.1.7 Toxicity Management

Subjects who develop a new infection while undergoing treatment with adalimumab should be monitored closely. Administration of study injections should be interrupted if subject develops an infection requiring IV anti-infective treatment or if an infection meets the definition of "serious" (refer to Section 6.0 for definitions). Study medication may be restarted once the physician determines that the infection has been successfully treated. Otherwise prohibited concomitant medications may be given if medically necessitated. Specifically, if a subject develops an inter-current infection, then topical and/or oral antibiotic usage is permitted. Prior to use, every attempt should be made to contact the AbbVie Study Designated Physician for direction on re-introduction of adalimumab therapy after prohibited medication administration.

6.2 Product Complaint

6.2.1 Definition

A Product Complaint is any Complaint (see Section 6.0 for the definition) related to the biologic or drug component of the product or to the pre-filled syringe.

For a product this may include, but is not limited to, damaged/broken product or packaging, product appearance whose color/markings do not match the labeling, labeling discrepancies/inadequacies in the labeling/instructions (example: printing illegible), missing components/product, device (i.e., syringe not working properly, or packaging issues).

For a medical device (i.e., pre-filled syringe), a product complaint also includes deaths of a patient using the device, any illness, injury, or adverse event in the proximity of the device, an adverse event that could be a result of using the device, any event needing medical or surgical intervention including hospitalization while using the device and use errors.

Any information available to help in the determination of causality by the device to the events outlined directly above should be recorded.

6.2.2 Reporting

Product Complaints concerning the study drug and/or pre-filled syringes must be reported to the Sponsor within 24 hours of the study site's knowledge of the event via the Product Complaint form. Product Complaints occurring during the study will be followed-up to a satisfactory conclusion. All follow-up information is to be reported to the Sponsor (or an authorized representative) and documented in source as required by the Sponsor. Product Complaints associated with adverse events will be reported in the study summary. All other complaints will be monitored on an ongoing basis.

Product Complaints may require return of the product (i.e., syringe) with the alleged complaint condition. In instances where a return is requested, every effort should be

made by the Study Investigator to return the product within 30 days. If returns cannot be accommodated within 30 days, the study site will need to provide justification and an estimated date of return.

The description of the complaint is important for AbbVie in order to enable AbbVie to investigate and determine if any corrective actions are required.

7.0 Protocol Deviations

AbbVie does not allow intentional/prospective deviations from the protocol unless when necessary to eliminate an immediate hazard to study subjects. The Study Investigator and sub-investigators are responsible for complying with all protocol requirements, and applicable global and local laws regarding protocol deviations. If a protocol deviation occurs (or is identified) after a subject has been enrolled, the Study Investigator is responsible for notifying IEC/IRB regulatory authorities (as applicable), and the following AbbVie CRA(s) or alternate contact:

Primary Contact:

AbbVie Site Monitor (contact information per country to be provided)

Alternate Contact:

[name]
[name]

Office:

Mobile:

Email:

Such contact must be made as soon as possible to permit a review by AbbVie to determine the impact of the deviation on the subject and/or the study. Any significant protocol deviation affecting subject eligibility and/or safety must be reviewed and/or approved by the IEC/IRB and regulatory authorities, as applicable prior to implementation.

For the purposes of this protocol, reportable deviations are defined as:

- subject entered into the study even though she/he did not satisfy entry criteria,
- subject developed withdrawal criteria during the study but was not withdrawn,
- subject received the wrong study drug or an incorrect dose of study drug, or
- subject received excluded or prohibited concomitant treatment (e.g., medication, surgical intervention)

8.0 Statistical Methods and Determination of Sample Size

8.1 Statistical and Analytical Plans

The objectives of the statistical analyses are to evaluate the clinical safety and efficacy of adalimumab compared to placebo in subjects with moderate to severe HS who are scheduled to undergo excisional surgery for the 12-week period prior to surgery (Period A), the 2-week perioperative period (Period B) and during a 10-week post-surgical period (Period C). Complete, specific details of the statistical analysis will be described and fully documented in the Statistical Analysis Plan (SAP). The SAP will be finalized prior to the database lock and blind break.

8.1.1 Analysis Populations

The Intent-to-Treat (ITT) Population is defined as all subjects who randomised at the Baseline visit. A Per-protocol Population (PP), which excludes patients with significant protocol violations, will be defined if deemed necessary. The ITT Population and the PP population, if defined, will be used for the efficacy analysis. Of note, the surgery-related endpoints during Periods B and C will be analysed among the subjects who undergo surgery.

The Safety Population is defined as all subjects who are in the ITT Population and receive at least one dose of study drug. The Safety Population in each period will be used for

safety analysis. Of note, the surgery-related safety endpoints during Periods B and C will be analysed among the subjects who undergo surgery.

For efficacy analysis, subjects included in the ITT population will be analysed by treatment group as randomised. That is, all subjects will be included in the treatment group to which they are randomised, regardless of which treatment the subject actually received. Subjects included in the PP Population, if defined, will be analysed as treated. That is, if a subject receives that treatment that is not the randomised assignment during the entire participation of a period or study, the subject will be analysed according to the treatment that the subject actually received.

For safety analysis, subjects included in the Safety Population will be analysed by treatment group as treated. That is, if a subject receives treatment that is not the randomized assignment during the entire participation of a period or study, the subject will be analysed according to the treatment the subject actually received.

8.1.2 Planned Methods of Statistical Analysis

All statistical tests will be two-tailed with the significance level 0.05. All *P* values will be rounded to three decimal places. Descriptive statistics will be provided. These include the number of observations, mean, and standard deviation for continuous variables; and counts and percentages for discrete variables.

The analyses will be performed using Statistical Analysis Software (SAS[®], SAS Institute Inc., Cary, NC, USA).

8.1.3 Demographic and Baseline Characteristics

Demographic and Baseline characteristics of the study subjects will be summarized for each arm of the study using descriptive statistics. Statistical tests will be performed to assess the comparability of the two arms. Continuous variable will be analysed using one-way analysis of variance (ANOVA), and discrete variable will be analysed using Fisher's exact test.

8.1.4 Statistical Analyses of Efficacy

The efficacy analysis will be conducted in the ITT Population and PP Population, if defined.

Visit windows and the data handling convention for summarizing efficacy results will be defined in the SAP.

Missing data will be imputed using the following methods for the efficacy analyses in the ITT Population:

- **Non-Responder Imputation (NRI):** the NRI analysis will categorize any subject who has a missing value at a specific visit as non-responder for that visit. The NRI will be the primary approach in the analyses of categorical variables. For analyses up to Week 12, NRI will be applied using evaluations within the period.
- **Last Observation Carried Forward (LOCF):** The LOCF analyses will use the completed evaluation from the previous visit within the particular period for efficacy measures assessed to impute missing data at later visits in the same period. Baseline efficacy evaluations will not be carried forward. LOCF will be the primary approach in the analyses of continuous variables, and the secondary approach in the analyses of categorical variables.
- **As-Observed:** The As-observed analyses will not impute values for missing evaluations, and thus a subject who did not have an evaluation on a scheduled visit will be excluded from the As-observed analysis for that visit. As-observed analyses will be the secondary approach in the analyses of continuous variables.

Multiple Imputation (MI) for missing values will be performed for the primary efficacy variable.

Lesions that receive intervention (e.g., contained within the excised surgical specimen, protocol-allowed minor interventions including incision and drainage) will be counted as permanently present from the date of the intervention.

In order to evaluate the impact of major protocol violations on the results of the trial, efficacy assessments obtained after the start of a major protocol-disallowed treatment will be excluded from the analysis. Subjects will be counted as non-responders for the categorical variable from the date of the major protocol-disallowed treatment and have their LOCF for continuous variables. The exclusion of efficacy assessments will be determined via classification prior to the database lock.

Additional analyses may be performed for the primary efficacy variable adjusting for baseline covariates in addition to the stratification factors.

8.1.4.1 Primary Analysis of Efficacy

The primary analysis will be the comparison of the adalimumab ew treatment group versus the placebo treatment group in the proportion of subjects achieving HiSCR at Week 12. The number and percentage of subjects achieving HiSCR will be computed for each treatment arm and the difference in response rates (adalimumab – placebo) will be analysed using the Cochran-Mantel-Haenszel (CMH) test, stratified by the stratification factors used for randomization. The 95% confidence intervals of treatment difference will also be provided.

The primary analysis will be carried out in the ITT Population and the PP Population, if defined. Non-responder imputation will be used as the primary approach for missing values. LOCF and MI will be performed as sensitivity analyses for the primary efficacy variable.

In addition, a sensitivity analysis controlling for change from baseline in body weight using logistic regression models, for the primary efficacy endpoint. Analysis details will be specified in the SAP prior to study unblinding and prior to database lock.

8.1.4.2 Secondary Analyses of Efficacy

Categorical variables will be analysed by CMH adjusting for the stratification factors for randomisation. Continuous variables will be analysed by analysis of covariance

(ANCOVA) with Baseline value and the stratification factors used randomization in the model.

The analyses of the adalimumab ew group versus placebo group will be carried out in the ITT Population.

Additional analyses may be performed for the primary efficacy variable adjusting for baseline covariates. Results from any additional analyses will not be used as a substitute for the planned analyses, but may be used as supplemental information for the study report.

To evaluate the consistency of the efficacy over demographic and other baseline characteristics, summaries and analyses will be performed for selected subgroups for the primary endpoint and ranked secondary endpoints. The detailed subgroups will be outlined in the SAP.

8.1.5 Statistical Analyses of Safety

All AEs, SAEs, AEs leading to discontinuation, pre-specified AEs of special interest (AESIs) and adverse events concerning the surgical site will be collected during the study and up to approximately 70 days after the last dose of the study drug for subjects who do not elect to treat his/her HS disease with commercial adalimumab.

Safety analyses will be carried out using the Safety Population. Pretreatment AEs will be summarized. Any TEAE is defined as an event with onset or worsening after the first study drug administration and within approximately 70 days after the last study drug administration for subjects who do not elect to treat his/her HS disease with commercial adalimumab.

The number and percent of subjects experiencing treatment-emergent TEAEs will be tabulated using the Medical Dictionary for Drug Regulatory Activities (MedDRA[®]) system organ class and preferred term. Comparisons of the percentages of subjects experiencing an AE in the adalimumab group versus the placebo group will be performed

using Fisher's exact test for data collected in the entire study, and separately for Period A, Period B, and Period C. Summaries (including percentages and event per 100 patient-years) of SAEs, deaths, AEs leading to discontinuation from the study, AESIs, and adverse events concerning the surgical site will also be provided.

8.2 Determination of Sample Size

The study is designed to enroll approximately 200 subjects. Assuming the true treatment difference in this study population is at least 20%, 100 subjects per arm will provide at least 80% power to detect the treatment difference at the alpha level of 0.05. The study also has at least 80% power to demonstrate the point estimate of the treatment difference of at least 15%.

The response rates observed in the combined PIONEER I and II studies (Studies M11-313 and M11-810, respectively) for the HiSCR at Week 12 were 50.6% and 26.8% in the adalimumab ew group and placebo group, respectively. Due to the potential differences between the population of moderate-to-severe HS patients who are surgical candidates and the general moderate-to-severe HS patient population, a conservative estimate of 20% treatment difference is used for the power calculation.

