Subjects that initially screen fail for the study may be permitted to re-screen following re-consent. All screening procedures with the possible exceptions noted below will be repeated. The subject must meet all inclusion and none of the exclusion criteria at the time of re-screening in order to qualify for the study. There is no minimum period of time a subject must wait to re-screen for the study. If the subject had a complete initial screening evaluation including tuberculosis (TB) screening, chest x-ray (CXR, if applicable), and 12-lead electrocardiogram (ECG), these tests will not be required to be repeated for re-screening provided the conditions noted in Section 5.3.1.1 are met and no more than 3 months (90 days) have passed. As appropriate, study sites are encouraged to contact the AbbVie Medical Monitor to confirm if subjects should or should not be

re-screened. If the subject had a negative human immunodeficiency virus (HIV) result at screening but 30 days have elapsed prior to the re-screen, then the HIV screening test must be repeated and the result handled in a like manner as the original screening test (see Section 5.3.1.1).

Period A: A 12-week double-blind, placebo-controlled treatment period during which subjects are randomised in a 1:1 ratio to receive adalimumab or matching placebo, 160 mg initially at Day 1 (or given as two 40 mg injections per day for 2 consecutive days), followed by 80 mg 2 weeks later at Day 15 (given as two 40 mg injections in 1 day). Two weeks later (Day 29) continue with a dose of 40 mg ew until Week 12. The randomisation will be stratified by baseline Hurley Stage (II versus III) and anatomical location of the surgical site (i.e., axilla versus inguinal region). A subject's Hurley Stage is determined by the worst Hurley Stage (i.e., II versus III) across all affected anatomic regions. The projected size of the surgical excision established by the designated surgeon during the Screening Period (calculated from a tracing of the outer perimeter onto an acetate sheet or equivalent) will be recorded by the study physician in the CRF. On each clinical study visit day, all study procedures scheduled for that visit will be completed prior to study drug administration.

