### 4.4 Sample Size Justification

The study is designed to enroll approximately 200 subjects. Assuming the true treatment difference in this study population is at least 20%, 100 subjects per arm will provide at

least 80% power to detect the treatment difference at the alpha level of 0.05. The study also has at least 80% power to demonstrate the point estimate of the treatment difference of at least 15%.

The response rates observed in the combined PIONEER I and II studies (Studies M11-313 and M11-810, respectively) for the HiSCR at Week 12 were 50.6% and 26.8% in the adalimumab ew group and placebo group, respectively. Due to the potential differences between the population of moderate-to-severe HS patients who are surgical candidates and the general moderate-to-severe HS patient population, a conservative estimate of 20% treatment difference is used for the power calculation.

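### Does the statement of at least 80% power for an observed difference of at least 15 points fail at the planned 20-point difference?

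*Protocol*

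**What the plan says.** Protocol 8.2 makes two statements about 200 subjects. The first, for a true difference of 20 points or more, is that "100 subjects per arm will provide at least 80% power to detect the treatment difference at the alpha level of 0.05". The second concerns the size of the estimate: "The study also has at least 80% power to demonstrate the point estimate of the treatment difference of at least 15" percent. SAP 4.4 repeats it ("80% power to demonstrate the point estimate of the treatment difference of at least 15" percent), as does the Synopsis (Protocol 1.2).

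The same section cites earlier response rates "for the HiSCR at Week 12 were 50.6% and 26.8% in the adalimumab ew group and placebo group, respectively", a difference of 23.8 points. It says that surgical candidates may differ from the general moderate-to-severe population, and that for this reason "a conservative estimate of 20% treatment difference is used for the power calculation". Only the difference is carried forward. No planning placebo rate is named, nor any estimator (crude or stratum-weighted) or method for the second statement.

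**The concern.** A power claim worded as a floor should be reproducible at the planning values. A reader who takes the only placebo rate in the documents, adds the 20-point planning difference and applies the usual normal approximation gets about 77%, not 80%. The main power statement beside it reproduces without trouble, so the second looks like a slip that was then copied into two further places.

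If 15 points were a threshold for success or for clinical relevance, the chance of reaching it would be slightly overstated in the Synopsis, the protocol body and the SAP.

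**Working it through.** **Inputs**

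- 100 per arm; true difference 0.20; threshold 0.15 (Protocol 8.2, SAP 4.4).
- Equal allocation: "subjects are randomised in a 1:1 ratio to receive adalimumab or matching placebo" (Protocol 5.1.1).
- "All statistical tests will be two-tailed with the significance level 0.05" (Protocol 8.1.2). This matters only for the first statement; the second uses no alpha.
- No loss of denominator, because "the NRI analysis will categorize any subject who has a missing value at a specific visit as non-responder for that visit" (Protocol 8.1.4). The SAP 4.7 exception, for subjects who respond both before and after a visit, leaves the denominator unchanged.
- Placebo rate: not given. The historical 26.8% is an **assumption**, so the rates are 46.8% and 26.8%. It is varied below.

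**First statement (the plan's main figure)**

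Power = Φ[(0.20 − 1.96·SE₀)/SE₁], with pooled SE₀ under the null and unpooled SE₁ under the alternative.

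- 46.8% vs 26.8%: SE₀ = √(2 × 0.368 × 0.632/100) = 0.0682 and SE₁ = √((0.468 × 0.532 + 0.268 × 0.732)/100) = 0.0667. Power = Φ[(0.20 − 0.1337)/0.0667] = Φ(0.994) = 84.0%.
- 60% vs 40%: 81.2%.

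The statement of at least 80% is met at every placebo rate tried, from 5% to 40%.

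**Second statement: P(observed difference ≥ 0.15)** at 46.8% vs 26.8%, 100:100

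- Uncorrected normal: Φ(0.05/0.0667) = 77.3%.
- Continuity-corrected normal (cut-off 0.145): Φ(0.055/0.0667) = 79.5%.
- Exact sum over two independent binomials: 79.55%.

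With 100 per arm the observed difference moves in steps of 0.01, and exactly 15 points meets the criterion. The exact probability of strictly more than 15 points is 75.07%, so about 4.5 points of probability sit on 15 itself. The uncorrected approximation counts only about half of that. This explains why it falls 2.2 points below the exact value (79.55 − 77.3).

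**Dependence on the unstated placebo rate** (true difference 20 points, 100:100)

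| Placebo rate | Uncorrected normal | Exact |
|---|---|---|
| 10% | 81.9% | 84.3% |
| 15% | 79.9% | 82.2% |
| 20% | 78.5% | 80.8% |
| 23% | 77.9% | 80.2% |
| 25% | 77.6% | 79.8% |
| 26.8% | 77.3% | 79.55% |
| 30% | 77.0% | 79.2% |
| 40% | 76.5% | 78.7% |

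The exact figure crosses 80% at a placebo rate of about 23.9%, which is 2.9 points below the historical one. The uncorrected normal figure crosses at about 14.8%.

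**Dependence on the true difference** (placebo 26.8%)

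The exact figure reaches 80% at about 20.1 points and is 83.5% at 21 points. The uncorrected normal figure reaches 80% at about 20.6 points. At the cited rates of 50.6% and 26.8% the values are 91.7% exact and 90.6% normal.

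**Role of the 15-point estimate**

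SAP 4.6, 6.2 and 6.3 define the inference: a two-sided test of the primary endpoint at 0.05, then the ranked secondary endpoints in order. None of them refers to a 15-point estimate.

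**The case for a change.** The strongest case for acting is that a claim of at least 80% is a floor, and a floor must hold at the lower bound of its assumption. Protocol 8.2 names 20 points as the value used, so pointing to 23.8 points discards the plan's own conservative choice. Moreover, 79.55% is the most favourable of the nearby cases. With splits from 95:105 to 105:95 the exact figure ranges from 76.3% (at 99:101) to 79.55% (at 100:100), with a mean of 77.5%. Enrolment is only approximately 200 and randomisation is stratified, so an exact 100:100 split is not assured. A Mantel-Haenszel-weighted difference, the natural companion to the stratified test, gave about 77% in simulations allowing slight imbalance within strata, and 79.6% with four perfectly balanced strata of 50. Keeping the other cited rate (50.6% vs 30.6%) gives 76.9% normal and 79.1% exact. No variant that combines a cited rate with a 20-point difference reaches 80%.

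All of that arithmetic stands, and 20 points is the fair place to test the claim. It does not establish an error. Every variant rests on a placebo rate that the plan reports as history, from a population it says may differ, and does not adopt. The lower values also need unplanned splits, assumed strata or the approximation that omits the mass at exactly 15 points. Design statements are normally computed at the planned allocation, and there the exact and continuity-corrected results both round to 80%. What remains is that a reader cannot tell which rate, estimator and method lie behind the sentence.

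**Conclusion.** The concern does not call for a change. Under the assumed 26.8% placebo rate, a 20-point true difference and 100 per arm, the probability is 79.55% exact, 0.45 points below the stated floor; the uncorrected approximation puts the gap at 2.7 points. A planning placebo rate of about 23.9% or lower would make the sentence literally true by the exact method, and the documents neither state nor rule out such a rate.

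This is a gap in description around a supplementary sentence. Writing 46.8% and 26.8% into the plan would attribute to the sponsor planning rates it never stated. Softening the wording to about 80% would do no harm, but would alter no sample size, test, estimate or conclusion. Enrolment, primary power, alpha and the analyses all stand as they are. The judgement would differ if a 15-point estimate were a criterion for success, but neither document makes it one.
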